7.1.4 Post-Surgery until Hospital Discharge

Prior to discharge, the following data will be recorded:

- Physical examination as per the institution's normal procedure
- Changes in concomitant medications
- Adverse events, including reoperation, any complications possibly related to bleeding and/or thrombotic events
- Date of hospital discharge (for overall Length of Stay).

7.1.5 30-day Follow-Up Phone Call/Office Visit (+ 14 days)

The following information will be recorded at the clinical follow-up phone call or office visit approximately 30 days following the study surgery:

- Changes in concomitant medications, including use of any blood products following hospital discharge.
- Adverse events

7.1.6 6-Month Follow-Up Phone Call/Office Visit (+/- 30 days)

All treated subjects will receive a 6-month (+/-30 days) follow-up phone call or office visit to assess:

- Any SAEs requiring surgical intervention and assessed as having either a possible, probable or causal relationship to the study treatment. Detailed data on action taken for the SAE will not be reportable.

7.2 Procedures for Handling Biological Samples

7.2.1 Laboratory Tests

All laboratory investigations will be performed at the local hospital laboratory. The volume of blood to be taken will be determined according to the standard practices of each hospital. The normal reference ranges and laboratory accreditation certificates will be provided to the Sponsor.

7.3 Premature Withdrawal of Subjects for the Study

All subjects should be encouraged to remain in the study until they have completed all study required follow-up phone calls or office visits. Subjects may discontinue participation in the study at any time and for any reason. However, if the subject decides to discontinue participation in the study, the reason must be documented when possible. Reasons for early withdrawal include, but are not limited to:

- Consent withdrawn by the subject;
- Subject refusal to complete study follow-ups and/or procedures;
- Lost to follow-up: a recorded delivery letter will be sent to the subject at their last known address, after a minimum of three documented attempts to reach the subject by telephone have failed. If communication via certified letter is unsuccessful, the subject will be considered lost to follow-up;
- Adverse events; or
- Other reason, specify.

Subjects who discontinue from the study prematurely will not be replaced.

8 STATISTICAL METHODS

The Data Management and Biostatistics groups at Ethicon will be responsible for the overall analysis of data from this protocol. The detailed Statistical Analysis Plan (SAP) will be based on and will supplement the statistical design and analysis described in this section.

8.1 Sample Size Determination

No formal sample size determination was performed for this study; however, a sample size of 100 evaluable subjects is considered adequate to provide sufficient information to evaluate the safety and effectiveness outcomes using descriptive summaries. Although no inferential statistical analyses or hypothesis testing will be performed for the purpose of making claims in this study, a two-sided Clopper-Pearson 95% confidence interval for the proportion of successes will be reported for the primary effectiveness endpoint. Assuming a success rate of 85%, the estimation precision of the Clopper-Pearson two-sided 95% CI for the success rate (as measured by the half-width of the confidence interval) when the most likely number of successes (85) is observed, is 7.4%. Additionally, for evaluation of safety and observation of adverse events that occur at a rate as low as 2.5% in the population, a sample size of 100 subjects provides greater than 90% probability for observing at least 1 such adverse event. Thus, a sample size of at least 100 evaluable subjects should give reasonable assurance that the absence of such events in the study is not a result of too few patients being studied, should none be observed.

8.2 Data Analysis

The continuous data will be summarised descriptively by number of subjects, mean, standard deviation (SD), median, minimum and maximum. The categorical data will be summarised descriptively by frequency counts along with associated percentages.

8.2.1 Analysis Sets

The following three analysis sets are defined:

- Intent-to-Treat (ITT) analysis set consists of all subjects for whom TBS was identified. Subjects who do not complete the procedure after TBS identification will be included in the ITT.
- Per-Protocol (PP) (Evaluable) analysis set consists of all ITT subjects who have no major protocol deviations affecting the primary effectiveness endpoint and have data available for this endpoint.
- Safety analysis set consists of all subjects who received study product.

The primary effectiveness endpoint will be analysed using the ITT and the PP sets. However, the primary analysis will be based on the ITT set. The PP analysis will be considered supportive.

All secondary effectiveness endpoints (listed in section 8.3.1) will be analysed using the ITT set, while safety endpoints (listed in section 8.4.1) will be analysed using the Safety set.

It is not anticipated that there will be data missing for the primary or secondary effectiveness endpoints, but, if there is, the analyses based on the ITT set will consider missing data as failures for these endpoints. Missing data for safety endpoints will not be imputed.

Major protocol deviations will be determined prior to database lock.

8.3 Effectiveness

8.3.1 Effectiveness Variables

The following primary endpoint will be analysed using the ITT and per protocol sets:

- Proportion of subjects achieving haemostatic success at **5** minutes following the application of SURGICEL Powder with no re-bleeding requiring additional treatment at the TBS any time prior to initiation of final fascial closure.

The following secondary endpoints will be analysed using the ITT set only:

- Proportion of subjects achieving haemostatic success at **3** minutes following the application of SURGICEL Powder with no re-bleeding requiring additional treatment at the TBS any time prior to initiation of final fascial closure.
- Proportion of subjects achieving haemostatic success at **10** minutes following the application of SURGICEL Powder with no re-bleeding requiring additional treatment at the TBS any time prior to initiation of final fascial closure.

8.3.2 Methods of Analysis

For binary (success/failure) primary and secondary effectiveness endpoints (3, 5, and 10 minutes haemostasis endpoints), the number and percentage of subjects with treatment success as well as the two-sided Clopper-Pearson 95% CI around the proportion of successes will be reported. Missing outcomes in the ITT set will be treated as effectiveness failures. No inferential statistical analysis will be performed for the effectiveness endpoints.

8.4 Safety

8.4.1 Safety Variables / Criteria

The safety endpoints for the study include;

- Incidence of thromboembolic events that were assessed as having either a possible, probable or causal relationship to the study treatment (from time of SURGICEL Powder application at TBS through 30-day follow-up via phone call or office visit);
- Incidence of post-operative re-bleeding that was assessed as having either a possible, probable or causal relationship to the TBS and requiring medical/surgical intervention (from initiation of final fascial closure through 30-day follow-up via phone call or office visit);
- Incidence of serious adverse events requiring surgical intervention and assessed as having either a possible, probable or causal relationship to the study treatment (from time of

SURGICEL Powder application at TBS through 6-month follow-up done via phone call or office visit)

8.4.2 Methods of Analysis

Adverse events will be summarised descriptively, using Medical Dictionary for Regulatory Activities (MedDRA) terminology.

Safety data will be summarised descriptively as described in section 8.2. No inferential statistical analysis will be performed for the safety endpoints.

8.5 HEOR (Health Economics & Outcomes Research)

Data collected in this study may be used in Health Economics and Outcomes Research (HEOR). In addition, data using the surgeon EUQ (Ease of Use Questionnaire), a tool validated in prior clinical trials, will also be collected.

HEOR data will be summarised descriptively as described in section 8.2. No inferential statistical analysis will be performed for the HEOR outcomes.

8.6 Schedule of Analyses

Two analyses will be performed. The first analysis will occur after all subjects complete phone call or office visit 1 [30 days (+ 14 days) post-surgery]. All data collected through 30-day (+14 days) follow-up will be analysed. The second analysis will occur after all subjects complete phone call or office visit 2 [6-month (+/-30 days) post-surgery] and the data collected at this follow-up is available. The second analysis will be performed on the data from the 6-month follow-up assessing any occurrences of SAEs requiring surgical intervention and assessed as having either a possible, probable or causal relationship to the study treatment

8.7 Handling of Missing Data

It is not anticipated that there will be data missing for the primary or secondary effectiveness endpoints, but, if there is, the analyses based on the ITT set will consider missing data as failures for these endpoints. Missing data for safety endpoints will not be imputed.

9 ASSESSMENT OF SAFETY

Sponsor's Medical Director (Study Medical Monitor/Safety Lead) will assess all serious adverse events for causality and expectedness and will utilise Ethicon's Product Safety Committee (PSC) to review and adjudicate the following safety signals:

- Thromboembolic events
- Postoperative re-bleeding
- Reoperations for complications assessed as having a possible, probable or causal relationship to the study treatment

The PSC will also review cumulative safety data from the study. The PSC will advise on the continuing safety of study subjects and those yet to be recruited to the study. Based on cumulative data from the study, the PSC may recommend whether to continue, suspend, modify, or stop the study. At the conclusion of the study, the PSC will also give a final assessment of the safety of the product from this study. The composition, responsibilities, frequency of PSC meetings, handling of emergency situations, and documentation of PSC meetings will be specified in the Safety Management Plan (SMP).

Stopping Rules:

The rules outlined below will be used to determine if the clinical trial should be put on hold contingent on PSC recommendations:

- If three confirmed thromboembolic serious adverse events (PE/DVT SAEs) are reported and assessed as being related to the study treatment.
- If one or more subject(s) develops post-operative bleeding and the TBS is confirmed as the cause of the re-bleeding. The relatedness of the SAE to the study treatment is to be determined by the following:
 - Findings at re-operation
 - Findings of TBS re-bleeding at autopsy (if applicable)

10 ADVERSE EVENTS

Adverse Events associated with the device, or the procedure, and incidents such as those specified in local laws and regulations will be captured and reported during this study. Monitoring of study sites by Sponsor personnel will ensure that adverse events and product complaints are documented.

The Sponsor will review reported AEs and SAEs according to the current Safety Management Plan.

10.1 Definitions

10.1.1 Pre-existing Condition

A pre-existing condition is one that is present at the start of the study, and is to be reported as part of the subject's medical history. It must be reported as a new Adverse Event if the intensity, frequency, or the character of the condition worsens during the study treatment.

To avoid confusing pre-existing conditions with AEs during data analysis, the study sites must make all attempts to provide start dates for all baseline medical conditions. Any pre-existing condition that has worsened in intensity, frequency, or the character of the condition should be recorded on the AE eCRF as an exacerbation of the pre-existing condition and the start date will be recorded as the time when the exacerbation occurred.

10.1.2 Enrolled Subject

A subject that has signed the informed consent form.

10.1.3 Treated Subject

A subject that has received SURGICEL Powder at TBS. Routine use of SURGICEL Powder is not included in this definition.

10.1.4 Evaluable Subject

A subject for whom the TBS was identified, who has no major protocol deviations that affect the primary effectiveness endpoint and has data for this endpoint.

10.1.5 Adverse Event

For this study, an AE is an untoward medical occurrence (sign, symptom or disease) in a subject or clinical trial subject and which does not necessarily have a causal relationship with the study medical device. An untoward medical occurrence includes any new, undesirable medical experience or worsening of a pre-existing condition.

SURGICEL Powder application at TBS through the 30-Day Follow-Up: All AEs, whether attributable to the device/procedure or not, are to be recorded in the eCRF and reported to the Sponsor.

10.1.6 Adverse Device Effect

An Adverse Device Effect (ADE) is an adverse event related to the use of a study medical device. This includes any adverse event resulting from insufficient or inadequate Instructions for Use, deployment, implantation, or operation, or any malfunction of the study medical device. An ADE may also include any event resulting from use error or from intentional misuse of the study medical device.

10.1.7 Unexpected Adverse Device Effect

An unexpected ADE is an adverse device effect, the nature or severity of which is not consistent with the applicable product information (e.g. Investigator's Brochure or product labelling).

10.2 Serious Adverse Event

It is the Investigator's responsibility to determine the "seriousness" of an AE using the protocol defined terms below. An SAE is any AE that results in any of the following:

- Death or a life-threatening event.
- Inpatient hospitalisation or prolongation of hospitalisation.
- Persistent or significant disability/ incapacity.
- Congenital anomaly/ birth defect.

Notes:

1. For this protocol, adverse events of special interest (AESI) include: thromboembolic events, post-operative re-bleeding from the TBS, and re-operations for conditions considered as having either a possible, probable or causal relationship to the study treatment. If the AESI does not meet any other seriousness criteria it will still be considered serious as defined by medically important event criterion.

2. “Death” should not be reported as an AE. The cause of death should be reported as an AE. The only exception is “Sudden Death”, when the cause is unknown.
3. Planned hospitalisation for a pre-existing condition is not considered an SAE.
4. A procedure required by the protocol is not considered an SAE, unless the subject experiences a serious deterioration in health or hospitalisation is prolonged.

SURGICEL Powder application at TBS through 30-Day Follow-Up: All SAEs, whether attributable to the device/procedure, are to be recorded in the eCRF and reported to the Sponsor.

6-Month Follow-Up: SAEs requiring surgical intervention and assessed as having either a possible, probable or causal relationship to the study treatment are to be recorded in the eCRF and reported to the Sponsor.

Follow-up on all SAEs assessed as having either a possible, probable or causal relationship to the study treatment, which were ongoing at the 30-day post-surgery follow-up will be assessed.

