10.4 Relationship/Attribution of Adverse Events

It is the Investigator's responsibility to assess the relationship of an AE to the study procedure and study device(s).

The following guideline should be used in determining the relationship of an adverse event to the study device, study procedure, or other causality:

- **NOT RELATED**
- **UNLIKELY**
- **POSSIBLE**
- **PROBABLE**
- **CAUSAL RELATIONSHIP**

Refer to the Adverse Event Causality Assessment Guide in Appendix 3, Section 15.3 for detailed guidance on determining the relationship.

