10.5 Reporting Adverse Events

SURGICEL Powder application at TBS through 30-Day Follow-Up: All adverse events (both serious and non-serious), whether attributable to the device/procedure or not, will be reported from time of SURGICEL Powder application at TBS until completion of the 30-day follow-up. The Investigator will evaluate the severity of the event, and its relatedness to the study device or procedure and the information will be entered in the AE eCRFs.

6-Month Follow-Up:

Follow-up on all SAEs that Investigator reported as having either a possible, probable or causal relationship to study treatment, which were ongoing at the 30-day post-surgery visit will be assessed.

SAEs requiring surgical intervention and assessed as having either a possible, probable or causal relationship to the study treatment will be reported at the 6-month follow-up. The Investigator will evaluate the severity of the event, and its relatedness to the study device or procedure and the information will be entered in the AE eCRFs.

Any necessary medical management of the event will be recorded in the subject's medical record/source document.

The Investigator will record all AEs (both serious and non-serious) in the source documents. CTC (Common Terminology Criteria) should be used when recording AEs. In addition, the following information should be recorded:

- Onset date
- Resolution date or date of death
- Severity of the event

- Action taken
- Event status (ongoing at study end or resolved)
- Relationship of AE to the study treatment
- Relationship of AE to the study procedure
- Indication of seriousness

Reporting Serious Adverse Events to the Sponsor

SURGICEL Powder application at TBS through 30-Day Follow-Up:

The study site must report all SAEs, whether they are related to the device or procedure, to the Sponsor as soon as possible, but no later 72 hours of becoming aware of the SAE.

6-Month Follow-Up:

The study site must report SAEs requiring surgical intervention and assessed as having either a possible, probable or causal relationship to the device or procedure to the Sponsor as soon as possible, but no later 72 hours of becoming aware of the SAE.

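### After the 30-day contact, only SAEs that the Investigator has already judged related reach the Sponsor, and section 10.5 states that filter in two different ways

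*Protocol*

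**What the plan says.** Section 8.4.1 defines the third safety endpoint as "Incidence of serious adverse events requiring surgical intervention and assessed as having either a possible, probable or causal relationship to the study treatment", counted from application of the powder through the 6-month contact.

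Up to the 30-day contact, sections 10.2 and 10.5 require every SAE to be entered in the eCRF and sent to the Sponsor regardless of cause.

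For the 6-month contact, section 10.2 limits eCRF entry: "SAEs requiring surgical intervention and assessed as having either a possible, probable or causal relationship to the study treatment are to be recorded". The schedule of activities (last row and footnote 6) and section 7.1.6 set the same limit. So does the first 6-month paragraph of section 10.5, where events "assessed as having either a possible, probable or causal relationship to the study treatment will be reported at the 6-month follow-up". Related SAEs still ongoing at the 30-day contact are also followed up. Section 7.1.6 adds: "Detailed data on action taken for the SAE will not be reportable".

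The later part of section 10.5, on reporting SAEs to the Sponsor, uses a different test at 6 months. It covers surgical SAEs "assessed as having either a possible, probable or causal relationship to the device or procedure to the Sponsor". The same section lists relationship to the study treatment as one data item and "Relationship of AE to the study procedure" as another.

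Section 10.4 makes the Investigator responsible for the relationship assessment. Section 9 says that the Sponsor's Medical Director "will assess all serious adverse events for causality and expectedness", with the Product Safety Committee (PSC) adjudicating listed signals.

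**The concern.** One incidence is being collected under two capture rules. In the first part, attribution is a field on a recorded event, and the Sponsor can review it. In the second part, attribution is the condition for the event being recorded in the eCRF at all. The person who sets it is the Investigator, who under section 7.1.3 calls out completion of the application, in an open-label study with no control arm.

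The 6-month contact and the second analysis (section 8.6) exist for this endpoint. If the classification that defines the endpoint cannot be checked for most of its time window, a low or zero count is hard to interpret. Separately, a site that reads section 10.5 closely finds two incompatible instructions for the same late event.

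**Working it through.** **Step 1. Which late events are captured.** Take an SAE requiring surgical intervention and read device and study treatment as the same thing.

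| Investigator's attribution | Up to the 30-day contact | After it: schedule, 7.1.6, 10.2, first 6-month paragraph of 10.5 | After it: 10.5, rule for reporting to the Sponsor |
|---|---|---|---|
| At least possibly related to treatment | Recorded and reported | Recorded and reported | Reported |
| Procedure only | Recorded and reported | Not captured | Reported |
| Neither | Recorded and reported | Not captured | Not captured |

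The second row is the contradiction. The third row is the gap under either rule.

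**Step 2. Effect on Sponsor review.** Section 9 promises Sponsor assessment of all SAEs. Before the 30-day contact it can move an event in either direction. Afterwards, third-row events have no stated route to it, and under the narrower rule neither do second-row events. For events that are not sent, no upward revision is possible.

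**Step 3. Effect on the endpoint count.** The numerator in 8.4.1 is limited to events related to the study treatment. Treatment and procedure are separate fields in 10.5, so a procedure-only event reported under the wider rule can be identified and left out. The conflict makes reporting uneven between sites; it does not add to the count. Any error in the count therefore runs towards understatement, and only if an event held back would have been judged related on review. Section 8.4.1 does not say whose assessment counts. If only the Investigator's does, the loss is that the classification cannot be verified.

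**Step 4. Share of the window under the filter.** Taking 6 months as 180 days: (180 − 30)/180 = 5/6. With the visit windows (30-day contact at day 30 to 44, last contact at day 150 to 210), it runs from (150 − 44)/150 = 71% to (210 − 30)/210 = 86%.

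**Step 5. The plan's own safety figure.** Section 8.1 states a greater than 90% probability of seeing at least one event at a true rate of 2.5% in 100 subjects. Check: 1 − 0.975^100 = 92.05%, so the statement reproduces. It presumes that every event is captured. Let c be the share of true events captured over the whole period (an assumption, as the protocol gives none). The probability becomes 1 − (1 − 0.025c)^100:

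- c = 0.95: 91.0%
- c = 0.90: 89.7%
- c = 0.75: 84.9%
- c = 0.50: 71.6%

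It drops below 90% when c < (1 − 0.1^(1/100))/0.025 = 0.9105, that is, when more than about 9% of true events are lost. Events before the 30-day contact are all captured, so the share of late events lost would have to be larger than 9% to reach that point. Section 8.1 speaks of adverse events in general, so this only gives scale.

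**Step 6. Scale for a zero count.** Exact two-sided 95% upper limits with n = 100: 0 events, 1 − 0.025^(1/100) = 3.62%; 1 event, 5.45%; 3 events, 8.52%. These show what one or three recovered events would do. They do not estimate how many there are.

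**The case against.** The filter matches the endpoint and is openly stated as the purpose of the 6-month contact. This is a descriptive post-market study of a CE-marked product that section 6.1 describes as absorbed in about two weeks, and all events are collected unfiltered until the 30-day contact, which may be as late as day 44. Narrower collection after that is a defensible economy. The threshold is also low: Appendix 3 counts a weak relationship that cannot be ruled out as possible, and assigns cases that cannot be assessed to the same category. All of this stands, and it limits the likely harm. It does not help where the Investigator has actively judged an event unlikely or unrelated, and it does not resolve the two rules in 10.5.

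Section 9's reference to all SAEs could be read as all reported SAEs. That reading removes the literal conflict, but the review still covers late events only after the Investigator has selected them.

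A reader might infer more than the text supports:

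- That nothing is recorded. Section 10.5 puts all AEs in the source documents, 12.3.4 asks for thorough documentation, and 12.6.1 has monitors inspect those documents. What is missing is a rule that sends the event on for causality review.
- That the wider wording inflates the endpoint. Step 3 shows that it does not.
- That the PSC loses a review it has earlier in the study. Its re-operation remit in section 9 is conditional on relatedness at every time point. The Medical Director's assessment is the safeguard affected.
- That a particular number of re-operations will be missed. The protocol gives no rate of late re-operation or of misattribution.

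**Conclusion.** The point holds in two parts. First, after the 30-day contact, capture in the eCRF and reporting to the Sponsor depend on the Investigator's prior attribution, so for about five-sixths of the window (71% to 86% across the visit windows) the classification behind the endpoint cannot be checked upward. Second, the 6-month rules in 10.5 disagree on whether a procedure-only re-operation is reportable; that is an error as written.

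Any bias in the count would be towards understatement, and its size cannot be derived from the documents. The figures in steps 5 and 6 rest on assumed losses and show sensitivity only. Defining the endpoint by relatedness is legitimate and is not criticised here. This is an inexpensive correction that should be made; it does not invalidate the study.

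**What to change.** - In the schedule row and footnote 6, and in 7.1.6, 10.2 and 10.5, require that every SAE requiring surgical intervention since the 30-day contact be recorded and reported regardless of attribution.
- Record the Investigator's relationship to the study treatment and to the procedure as two separate entries.
- Use this single wording in both 6-month rules of 10.5, replacing both the study-treatment and the device-or-procedure tests.
- Have the Medical Director assess causality for these events as for earlier SAEs, and refer those assessed as related to the PSC.
- Leave the endpoint definition in 8.4.1 unchanged.

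The cost is protocol wording and a few more eCRF entries at a contact that already takes place, with no new visits. The downside is a small number of unrelated re-operations to enter and review.
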